Abbreviations: ED = exposure days; EPD = electronic patient diary; FVIII = factor VIII; ITI = immune tolerance induction; MTP = minimally treated patients; PUP = previously untreated patients; RAVE = data base for electronic case report

- a The scheduled study visits are shown in the table. Unscheduled visits are permitted at any time at the discretion of the investigator.
- b For MTPs, the Screening visit should only take place after a washout period of at least 72 hours following any previous treatment with any FVIII replacement product.
- c This visit is required only for PUPs and MTPs who have less than 40 ED, 6 months after the Baseline visit. The intent is to have at least one scheduled visit between completion of 20 ED and the expected date of accumulating 50 ED. The primary purpose of the visit is to assess the well-being of the participant, ensure continued compliance with the treatment, and make any needed adjustments in dosage or infusion frequency based upon weight or bleeding events.
- d For participants who do not develop high-titer FVIII inhibitor, the Final visit can be performed as soon as a minimum of 50 ED is achieved, but no later than 2 weeks after achieving 50 ED.
- e This follow-up is not required for study participants who develop high-titer inhibitor and continue in the study in the Optional ITI Treatment (Section 10.5.1).
- f Height/length and weight will be obtained for all participants at screening and at all subsequent visits.
- g Prior medications will be recorded at screening as part of medical history. Concomitant medications will be recorded at subsequent visits.
- h Inhibitor is to be evaluated at screening and in repeat sampling at least 1 week but not more than 2 weeks after screening (local laboratory testing) in MTPs only (i.e., unnecessary to be evaluated in PUPs). For MTPs, FVIII level and presence of FVIII inhibitor should be measured at least 72 hours after the last dose of FVIII. For MTPs, study drug administration should start upon availability of result from local laboratory testing documenting negative inhibitor titer.
- i Baseline inhibitor testing will be done in MTPs only.

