- j Study intervention will be administered throughout the study in accordance with the assigned prophylaxis regimen. Drug dispensing will be done in accordance with the individual drug dispensing schedule. Additional drug dispensing visits could be performed between Visit 6 and the Final visit in order to ensure study participants have sufficient study drug to cover the period between the scheduled study visits.
- k The EPD may be given to the parent/caregiver to take home at any time between the Screening and Baseline visits, but no entries should be made before the first infusion of study drug at the Baseline Visit.
- l Blood samples for FVIII level will be taken pre-infusion and at 15 to 30 minutes after end of infusion to calculate recovery at the Baseline visit and Visits 6 and 8 (Final visit). Infusion doses for recovery measurements must be given in hospital and directly reported in RAVE. The bioanalysis will be done at a local laboratory.
- m For PUPs who do not start treatment with study drug at the Baseline, recovery evaluation should be done at the study visit when prophylaxis is started.
- n Standard laboratory assessments include hematology and clinical chemistry. Guidance for blood draws in participants ≤10 kg is provided in Section 10.2.
- o Inhibitor will be evaluated at every visit after the start of treatment with study drug for MTPs as well as for PUPs. FVIII level and presence of FVIII inhibitor should be measured at least 48 hours after the last dose of study drug. The first positive inhibitor test after start of treatment with study drug must be confirmed by analysis of a second sample and by analysis of FVIII level recovery within 2 weeks of the investigator's notification.
- p Study center staff will call the parents/caregivers of participants approximately every 2 weeks between Baseline and Visit 8 (Final visit) and approximately 2 weeks after the last visit to verify proper completion of the participant diary and to review any new AEs and changes in concomitant medication since the last study visit.

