#### 4.4 End of Study Definition

A participant is considered to have completed the study if he has completed the last study visit, as shown in the Schedule of Activities for Part A (Section 1.3.1) or Part B (Section 1.3.2), or optional ITI treatment (Section 10.5.2).

Completion of Part A is when the last participant in Part A completes the final visit or early termination as shown in the Schedule of Activities for Part A (Section 1.3.1).

Completion of Part B is when the last participant in Part B completes the final visit or early termination as shown in the Schedule of Activities for Part B (Section 1.3.2).

Study participants who develop high-titer FVIII inhibitor and decide to enter optional ITI treatment with study intervention will discontinue participation in either Part A or Part B and complete the Early Termination visit. The end of study for these participants is defined as completion of the Optional ITI Treatment (Section 10.5.1).

Study participants who develop high titer FVIII inhibitor and decide to receive ITI with another product outside of the study will complete the Early Termination visit and leave the study.

The study itself will be considered complete after the last visit of the last participant for all centers has occurred.

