### 7.2.2 Visit 2/Baseline (No Later Than 4 Weeks From Visit 1)

For MTPs, this visit will include the first administration of study drug.

For PUPs, the first dose of KOVALTRY may be for treatment of a bleed. First treatment should not occur during high risk situations, surgery, or bleeds requiring prolonged or intensive treatment (see Section 6.6.2).

The following activities will be performed:

- Inclusion/exclusion criteria verification, i.e., confirmation of eligibility including check of laboratory test results.  
Note: MTPs must be inhibitor negative as evaluated via local laboratory testing at the Screening visit. A confirmatory inhibitor test must be taken at least 1 week but not more than 2 weeks after the Screening visit. Results from local laboratory testing must be negative ( $<0.6$  BU/mL) prior to administration of study intervention.
- Height/length and weight
- Vital signs (including systolic and diastolic blood pressure, heart rate, and body temperature); blood pressure may be deferred if the appropriate cuff size or equipment is not available (see Section 8.2 for details)
- Concomitant medication review
- Blood sampling before administration of study drug intervention
  - FVIII inhibitor assessment (Section 8.10; not required for PUPs but required for MTPs)

- In-hospital administration of the first dose of study drug (for MTPs and PUPs who are starting treatment at baseline).  
Note: First exposure to study drug may be either for treatment of an uncomplicated bleed or for start of prophylaxis. Inhibitor testing is mandatory every 3 to 5 ED until 20 ED are accumulated (see Section 6.6.2).
- Blood sampling after administration of study intervention (Section 7.3.2):
  - Incremental recovery (15 to 30 minutes post infusion) only for participants who start prophylaxis at Baseline; for PUPs who do not start prophylaxis at baseline, recovery should be done when prophylaxis is started
  - AE review
  - Study drug dispensation for home infusions in accordance with the IxRS drug dispensing schedule
  - Diary training review; participants/caregivers will be instructed to complete the EPD as required (see Section 7.3.1) beginning at Baseline through the end of the study (see Section 4.4)
  - Instruction on the prophylaxis regimen to be administered to the participant
  - Begin regular biweekly contact between the participant's parent/caregiver and the site to check EPD documentation and AE review until the End of Study/Early Termination

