## 10.5 Appendix 5: Optional Immune Tolerance Induction Treatment

### 10.5.1 Optional ITI Treatment for Participants who Develop High-Titer Inhibitors During the Study

If the option to receive ITI with the study intervention is made, the participant will discontinue participation in either Part A or Part B and continue in the Optional ITI Treatment, during which ITI will be provided at a dose of up to 200 IU/kg daily for up to a maximum of 18 months or until failure. A separate signed informed consent is required.

Initiation of ITI therapy (ITI Visit 1) should occur no later than 4 weeks from the date of notification by the investigator of the high-titer inhibitor development. In patients with a peak inhibitor titer  $>10$  BU/mL, it is recommended to postpone initiation of ITI until the inhibitor titer drops to  $\leq 10$  BU/mL. It is recommended to monitor the inhibitor titer monthly. In patients with a peak inhibitor titer  $>10$  BU/mL who experience serious or life-threatening bleeding or have frequent mild to moderate bleeding and are being considered for bypassing agent prophylaxis, an earlier start to ITI may be considered to avoid the morbidity associated with ongoing bleeding.

Response to ITI therapy may be observed earlier than 18 months and is defined as having no detectable inhibitor based on Nijmegen assay ( $<0.6$  BU/mL) and FVIII recovery of  $>66\%$  of predicted value. Failure is defined as no response ( $<20\%$  decrease in the inhibitor level) within a 6-month period after the initial 3 months of ITI and in the absence of any infection. In case of failure, ITI should be discontinued, and the Early ITI Termination visit will occur.

During the Optional ITI Treatment, failure to adhere to follow-up visits as per protocol (see Section 10.5.2) will lead to discontinuation of ITI support.

At the investigator's discretion, the participant may stop ITI with study drug. The Early ITI Termination visit should be done if the decision is made by the investigator/participant to stop ITI prior to documented negative inhibitor titer.

For analysis of Optional ITI Treatment data, see Section 9.3, Section 9.4.1, and Section 9.4.4. Efficacy (ABR) will not be analyzed for ITI patients. Safety will be analyzed separately for the ITI treatment set.

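### Part B waives the two-week safety call for children going on to ITI without requiring that ITI has begun, so a child whose ITI is postponed can have no scheduled AE or medication contact

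*Protocol*

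**What the plan says.** **Leaving Part B.** Under Protocol Section 4.4, a high-titer participant who decides on ITI with study drug "will discontinue participation in either Part A or Part B and complete the Early Termination visit". The section adds: "The end of study for these participants is defined as completion of the Optional ITI Treatment". Nothing dates the Early Termination visit relative to ITI Visit 1.

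**Contacts in Part B.** Note p of Section 1.3.2 sets phone calls "approximately every 2 weeks between Baseline and Visit 8 (Final visit) and approximately 2 weeks after the last visit". Section 7.2.2 describes the regular site contact as running "to check EPD documentation and AE review until the End of Study/Early Termination". The one later call (Section 7.2.9) asks about new AEs and changed medication, FVIII products included.

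**The waiver.** Note e of Section 1.3.2 states: "This follow-up is not required for study participants who develop high-titer inhibitor and continue in the study in the Optional ITI Treatment". The Synopsis (Study Visits) and Section 4.1.2 make no such exception and give the call to all Part B families. SAP Section 3 repeats the Section 4.1.2 promise.

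**Start of ITI.** In Section 10.5.1 the start of ITI is ITI Visit 1, which "should occur no later than 4 weeks from the date of notification" of the high-titer inhibitor. For a peak above 10 BU/mL, however, "it is recommended to postpone initiation of ITI until the inhibitor titer drops to" 10 BU/mL or below. No longest wait is given. Monthly titers are recommended. If bleeding is serious or frequent, "an earlier start to ITI may be considered to avoid the morbidity associated with ongoing bleeding".

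**Contacts in ITI.** In Section 10.5.2, AEs and concomitant medication are first reviewed at ITI Visit 1, and phone calls about every four weeks run between ITI visits.

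**The concern.** The waiver makes sense when ITI starts promptly, because the ITI visits then replace the call. It does not allow for the postponement that Section 10.5.1 itself recommends. In that case the last scheduled Part B safety contact is removed while the contact meant to replace it is put off for an unstated time.

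The child concerned is still in the study, has a high-titer inhibitor and may be receiving bypassing agents. Two things are at stake. Non-serious AEs and bypassing-agent use may be recorded late, or by recall at ITI Visit 1. In addition, Section 10.5.1 makes bleeding during the wait a ground for starting ITI sooner, and a site without regular contact is less well placed to notice it.

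**Working it through.** The plan states no figure for this point, so the check is a count of scheduled AE or medication contacts between Early Termination and ITI Visit 1.

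1. Two-weekly Part B calls (Section 1.3.2, note p): they end at Visit 8/Early Termination, so 0.
2. Follow-up call (Section 7.2.9): 0 if note e applies, 1 if the Synopsis and Section 4.1.2 prevail. It falls due 2 weeks ± 7 days after the visit.
3. ITI visits and ITI calls (Section 10.5.2): none before ITI Visit 1, so 0.
4. Monthly titers (Section 10.5.1): recommended only, with no AE or medication review attached, so 0.

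Total: 0 + 0 + 0 + 0 = 0 with note e, or 0 + 1 + 0 + 0 = 1 without it. Whether this matters depends on the length of the gap:

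| Situation | Gap | Contacts with note e | Contacts if the call is made |
|---|---|---|---|
| Early Termination just before ITI Visit 1 | about none | none needed | none needed |
| Early Termination when ITI is chosen, peak ≤10 BU/mL | at most about 4 weeks | 0 | 1, unless ITI Visit 1 comes first |
| Early Termination when ITI is chosen, peak >10 BU/mL, ITI postponed | no upper limit stated | 0 | 1 |

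The third row is the case of interest. Restoring the call helps there only at about two weeks, and the rest of a long wait remains uncovered.

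**How many children.** Protocol Section 9.2.2 assumes an inhibitor rate of 35% to 54% in 6 children. Its own figure reproduces: the chance of at least one inhibitor is 1 − 0.65^6 = 92.5% at 35% (stated as at least 92%), and 1 − 0.46^6 = 99.1% at 54%. The expected number with any inhibitor is 6 × 0.35 = 2.1 to 6 × 0.54 = 3.2. This is a ceiling on the expected number affected. A child must also be high-titer, choose ITI within the study, peak above 10 BU/mL and have ITI postponed, and the documents give none of those proportions.

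**Effect on the analyses.** Section 9.4.1 excludes ITI data from efficacy. Section 9.4.4 closes the treatment-emergent window three days after the last Part B infusion, so events starting later in the wait are not Part B TEAEs.

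**The case against.** The strongest reply is that note e does not yet apply. It exempts children who continue in ITI, and ITI needs a separate consent, scheduled at ITI Visit 1. A waiting child may have neither consented nor started. This is a fair reading, and it means the note is ambiguous rather than plainly wrong. But Section 4.4 moves the child out of Part B on the decision to enter ITI, and the note does not tell the site which reading to use when the call falls due during the wait. Even on the favorable reading, only one call is gained.

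A second reply combines the Section 7.2.2 contact wording with the Section 4.4 definition of end of study, so that contact would run to completion of ITI. Note p cuts against this, because it ends the two-weekly calls at Visit 8, and Early Termination has by then taken place.

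Third, nothing forbids holding Early Termination just before ITI Visit 1, which closes the gap. That stands: the gap is possible, not inevitable.

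Fourth, a reader might infer that these children are left without safety oversight. The documents do not support that. The confirmed inhibitor is a mandatory serious event of special interest (Section 8.4.7). It must be followed whatever its cause (Section 8.4) and until it resolves or stabilizes (Section 8.4.3). SAE updates are due within 24 hours (Section 8.4.1), all medication after consent is to be recorded (Section 6.5), unscheduled visits are allowed, and monthly titers imply some site contact. These duties stand and limit the point. They do not remove it: the Section 8.4.3 duty works through later visits and contacts without scheduling any, SAE reporting depends on the site becoming aware, and the titers are optional.

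**Conclusion.** The point holds in a limited form. Note e conflicts with the Synopsis and Section 4.1.2 and is not tied to ITI having begun. A child whose Early Termination visit is held early and whose ITI is postponed can have no scheduled AE or medication contact during a wait of unstated length, or one call if the other sections govern. What is lost is timely, scheduled capture of non-serious AEs and bypassing-agent use.

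The conclusion assumes that Early Termination is held when ITI is chosen and that the recommended postponement is followed. It does not say that every ITI entrant goes uncontacted: at a peak of 10 BU/mL or less the interval is at most about four weeks, the same as the call interval within ITI. Nor does it support any inference of bias in the results. No ABR result changes, and the effect on the Part B TEAE tables is little or none. The number of children affected is below 2.1 to 3.2 in expectation and may be zero. This is a cheap improvement of low priority.

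**What to change.** Reword note e so that the call is waived only if ITI Visit 1 has taken place by the time the call is due. Otherwise make the call, and then review AEs, bleeds and concomitant medication (bypassing agents included) about every four weeks, for example alongside the monthly titer, until ITI Visit 1 or a decision not to start ITI. Align the Synopsis and Section 4.1.2 with the revised note so that all three agree.

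The cost is a short protocol wording change and a few extra calls for very few children, possibly none. No analysis needs to change.

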## 2. Introduction

KOVALTRY (BAY 81-8973), antihemophilic factor (recombinant), is a recombinant, human DNA sequence derived, full length Factor VIII concentrate indicated for use in adults and children with hemophilia A (congenital Factor VIII deficiency). As described in the KOVALTRY Prescribing Information in China (provided as an attachment in Section 12), KOVALTRY temporarily replaces the missing clotting factor VIII needed for effective hemostasis in patients with hemophilia A. Upon activation of the clotting cascade, FVIII is converted to activated FVIII and acts as a cofactor for activated factor IX, accelerating the conversion of factor X to activated factor X on phospholipid surfaces, which ultimately converts prothrombin to thrombin and leads to the formation of a fibrin clot.

The multinational clinical development program for KOVALTRY (LEOPOLD) included 3 clinical studies (LEOPOLD I, LEOPOLD II, and LEOPOLD Kids) that have demonstrated efficacy and safety for preventing and treating bleeding episodes in approximately 240 children, adolescents, and adults with severe hemophilia A across different populations and different regions of the world, including 6 Chinese participants in the LEOPOLD I study (PK evaluation part) and 23 adult/adolescent Chinese patients in the LEOPOLD II study.

KOVALTRY is currently authorized to be marketed in CC countries including China under the proprietary name KOVALTRY.

### 2.1 Study Rationale

Based on efficacy and safety data from completed multinational studies with KOVALTRY and the consistent results for both PK and clinical efficacy/safety in 29 adult/adolescent patients with severe hemophilia A from China, KOVALTRY was conditionally approved for use in adults and children in China in July 2018 for:

- Routine prophylaxis to reduce the frequency of bleeding episodes
- On-demand treatment and control of bleeding episodes
- Perioperative management of bleeding

Approved dosing recommendations for routine prophylaxis (as prescribing information, Section 12):

- Adolescents and adults: 20 to 40 IU of KOVALTRY per kg of body weight two or three times per week
- Children  $\leq$ 12 years old: 25 to 50 IU of KOVALTRY per kg body weight twice weekly, three times weekly, or every other day according to individual requirements

Efficacy and safety of KOVALTRY for prophylaxis, treatment of bleeding episodes, and perioperative management of hemophilia A patients were demonstrated in the completed LEOPOLD clinical trials in previously treated severe hemophilia A patients and supported approval for use of KOVALTRY in the management of hemophilia A patients in 49 countries, including China. LEOPOLD I and LEOPOLD II studies included 6 and 23 previously treated Chinese severe hemophilia A patients, respectively. There were no Chinese hemophilia A patients enrolled into LEOPOLD Kids study.

As part of the China NDA post-approval commitment, the China CDE and NMPA requested additional efficacy and safety data in previously treated and previously untreated Chinese hemophilia A patients. As agreed with China CDE, Part A of this study will obtain additional efficacy, safety, and PK data for KOVALTRY in Chinese PTPs (children  $<$ 12 years of age

and adolescents/adults  $\geq 12$  years of age). Additionally, as per consultation with CDE, Part B of the study will obtain efficacy and safety data in Chinese PUPs/minimally treated patients (MTPs [children  $< 6$  years of age]).

In the event that the study is not be finalized in time for a report to be delivered for license renewal, an interim analysis will be performed with all available data.

## 2.2 Background

Hemophilia A is a congenital disorder in which mutations in the FVIII gene lead to a qualitative or quantitative deficiency of FVIII protein and activity resulting in prolonged bleeding after trauma and recurrent spontaneous bleeding episodes. The World Federation of Hemophilia's global survey 2016 (the most recent year for which statistics are available) reported 14,390 cases of hemophilia in China. Of these, 12,533 cases were hemophilia A.

Individuals with severe hemophilia A experience frequent, recurrent bleeding into the soft tissue and joints, resulting in joint damage and debility, and significant negative effects on their Quality of Life (QoL), psychosocial well-being, education, and financial condition.

Standard treatment for hemophilia A patients is the replacement of the missing protein by infusion of exogenous FVIII concentrates, either as plasma-derived FVIII (pdFVIII) or recombinant rFVIII concentrates. FVIII is an important component of normal coagulation, and the biologic behavior is similar across all populations. Treatment is specifically directed to achieve desired plasma FVIII levels. There is a direct correlation between plasma FVIII levels, coagulant activity, and clinical manifestations.

Treatment regimens are typically either on-demand therapy (given when a bleeding occurs) or prophylaxis (which consists of regular infusion of FVIII given at scheduled intervals (e.g., 2x per week, 3x per week) to prevent bleeding).

Standard prophylaxis using regularly scheduled infusions at doses and dose intervals sufficient to prevent bleeding events have been demonstrated to result in not only preservation of joint function and reducing the incidence of early disability and death, but also reduced frequency of intracranial hemorrhage, fewer hospital admissions, less joint surgery, and fewer missed days at work. These benefits are the direct result of continuously improving standard of care, earlier diagnosis, and start of prophylactic treatment, and was made possible by the greater availability of a safe and consistently available source of factor concentrates.

However, due to the diverse access to hemophilia treatment centers in different cities in China, the treatment approach mostly used for hemophilia A patients is on-demand treatment, especially for adult patients. Historically, lack of access to routine prophylaxis treatment in some Chinese regions increased the likelihood of joint damage and compromised health-related quality of life. Low dose secondary prophylaxis (10 IU/kg, 2 times per week, 10-30 IU/kg weekly) has been explored as a cost saving approach for the treatment of Chinese patients with hemophilia. Although the results of this approach have been encouraging, there remains the goal of establishing effective individualized prophylaxis and standardized care for Chinese hemophilia patients. In recent years, the proportion of prophylaxis use in pediatric patients is increasing.

